### 3. GENERAL INFORMATION

Objective	To quantify and provide a normative standard for refractive and visual outcomes in eyes with significant corneal astigmatism undergoing cataract surgery with the Alcon Toric ReSTOR lens. As well as to quantify the postoperative rotational stability of the IOL.
	The hypothesis is that the addition of toricity will not affect the general performance of the ReSTOR design. As such, it is expected that patients with a ReSTOR toric IOL that achieve a correction of their astigmatism will have visual acuity and visual quality similar to patients implanted with the non-toric ReSTOR models. The Toric ReSTOR lenses (+2.5 and +3.0) will result in a residual refractive cylinder similar to that observed in patients with non-clinically significant astigmatism treated with non-toric ReSTOR lenses. They will also provide excellent distance and near vision in the vast majority of patients; we expect 75% of patients will have 20/25 (0.1 logMAR) or better uncorrected visual acuity at distance and near. The Toric-ReSTOR lens will demonstrate rotational stability that meets or exceeds the recommendations established by the American National Standards Institute.
Test Article(s)	Alcon Toric-ReSTOR +2.5 and +3.0 models
Control Article(s)	None.
Sample size	64 eyes of 32 subjects at 1 clinical site
Study Population	Subjects $\geq$ 30 years of age presenting for cataract surgery or refractive lens exchange surgery who are interested in astigmatism reduction and presbyopia correction. Subjects must be eligible for bilateral multifocal toric lens implantation.
Number of sites	One
Study Design	Prospective, non-randomized, single-arm, single center, open-label study.
Masking	None

Variables

Primary:

- Residual refractive cylinder

Secondary:

- Monocular and binocular Uncorrected and Best-corrected distance, intermediate (60cm) and near (40cm) visual acuity
- Postoperative orientation changes with the Toric ReSTOR IOL up to 3 months after surgery.
- Binocular Uncorrected and Best-corrected defocus curve (3 month visit).
- Quality of vision, measured with a subjective questionnaire.

Duration / Follow-up    Preoperative to 3 months postoperative

## 5. INTRODUCTION

In the past, patients with significant corneal astigmatism undergoing cataract surgery were given only the option of a monofocal astigmatism-correcting intraocular lens (IOL). Recently, the US FDA has approved intraocular lenses for the correction of astigmatism and presbyopia; these include toric-accommodating, toric-extended depth of focus, and now toric-multifocal (Toric-ReSTOR) IOLs. Patients implanted with non-toric ReSTOR lenses (2.5 and/or 3.0) have exhibited very good vision and high rates of satisfaction with their vision at various distances. Until recently, patients with corneal astigmatism could not take advantage of this option without considering a secondary procedure such as a corneal relaxing incision or refractive surgery. (More than 0.50D of expected postoperative refractive astigmatism has been suggested to materially affect visual quality and satisfaction after multifocal IOL implantation.) The availability of toric versions of the ReSTOR 2.5 and 3.0 lenses now allows for multifocal implantation in eyes with corneal astigmatism.

Postoperative rotational stability is an important consideration with any toric IOL. In general, each degree of misalignment or misorientation of an IOL will decrease the intended astigmatic correction by 3.3%, reducing the resultant image quality. The American National Standards Institute has established an IOL rotation stability standard requiring at least 90% of lenses to exhibit less than 5 degrees of rotation. Recent single-piece IOL studies have shown the AMO toric monofocal platform exhibits less than 5 degrees of rotation in 94.1% of eyes at the 6 month period. Multiple studies reviewing the Alcon toric-monofocal platform reveal similar rotational stability, with 95-96% of lenses showing less than 5 degrees of rotation.

The expectation is that the addition of toricity will not affect the general performance of the ReSTOR design. As such, it is expected that patients with a ReSTOR toric IOL that achieve a correction of their astigmatism will have visual acuity and visual quality similar to patients implanted with the non-toric ReSTOR models.

## 6. OBJECTIVE(S)

The objective is to provide a normative standard for refractive and visual outcomes in eyes with significant corneal astigmatism undergoing cataract surgery with the Alcon Toric ReSTOR lens.

## 7. SUBJECTS

### 7.1. *Subject Population*

Eligible test subjects will be patients presenting for cataract surgery or refractive lens exchange surgery who are interested in astigmatism reduction and presbyopia correction. Subjects must be eligible for bilateral multifocal toric lens implantation.

A total of 32 subjects at one site will be enrolled. Both eyes of a subject will be enrolled. Subjects must meet the inclusion criteria. Prior to enrollment, subjects will be provided information on the study and asked to sign a patient information and consent form to participate. The patient information and consent form will be approved by an appropriate ethics committee.

### ***7.2. Inclusion Criteria***

Subjects are eligible for the study if they meet the following criteria:

**Note:** Ocular criteria must be met in the eligible eye.

- Bilateral visually-significant cataracts
- Gender: Males and Females.
- Age: 30 or older.
- Willing and able to provide written informed consent for participation in the study.
- Willing and able to comply with scheduled visits and other study procedures.
- have good ocular health, with no pathology that compromises visual acuity (outside of residual refractive error and cataract)
- Regular corneal astigmatism of 1.00D to 2.50D in both eyes
- Potential postoperative acuity of 20/25 or better

### ***7.3. Exclusion Criteria***

If any of the following exclusion criteria are applicable to the subject or either eye, the subject should not be enrolled in the study.

- Irregular astigmatism (e.g. keratoconus)
- Corneal pathology (e.g. opacities, EBMD, Fuch's dystrophy, etc.)
- Monocular status (e.g. amblyopia)
- Previous radial keratotomy, corneal refractive surgery or other corneal surgery (e.g. corneal transplant, DSAEK, lamellar keratoplasty)
- Previous anterior or posterior chamber surgery (e.g., vitrectomy, laser iridotomy)
- Moderate-to-advanced glaucoma
- Strabismus
- Use of arcuate incisions for astigmatism management at the time of surgery
- Diabetic retinopathy
- Macular pathology (e.g. ARMD, ERM, etc.)
- History of retinal detachment

- Subjects who have an acute or chronic disease or illness that would confound the results of this investigation (e.g., immunocompromised, connective tissue disease, clinically significant atopic disease, diabetes, and any other such disease or illness), that are known to affect postoperative visual acuity.
- Participation in (or current participation) any investigational drug or device trial within the previous 30 days prior to the start date of this trial.

The principal investigator reserves the right to declare a patient ineligible or non-evaluable based on medical evidence that indicates they are unsuitable for the trial.

Pregnancy has a known effect on the stability of refractions and visual acuity. As such, subjects who become pregnant during the study will not be discontinued but their data may be excluded from analyses of effectiveness.

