## 8. STUDY DESIGN

### 8.1. Study Design

This study is a prospective, single center, open clinical trial to evaluate visual acuity at distance, intermediate and near as well as rotational stability of the Toric-ReSTOR IOL for 3 months after cataract surgery. Patients will be bilaterally implanted, with the Toric ReSTOR +2.5D model implanted in the dominant eye and the Toric ReSTOR +3.0D model implanted in the non-dominant eye. Patients will self-select for multifocal implantation. Toric IOL calculations will be completed with the Alcon Toric calculator, including the Barrett adjustment for posterior corneal astigmatism. The default surgically-induced astigmatism (0.1D) will be used for all calculations. Results from this study will be compared to outcomes data in the literature for the non-toric ReSTOR IOLs. Quality of vision will be measured using a validated, Rasch-scored questionnaire and compared to data available in the literature for non-toric ReSTOR lenses.

Subjects will be assessed pre-operatively and at 1 day, 1 week, 1 month and 3 months post-operatively.

Clinical evaluations will include measurement of visual acuity, manifest refraction, orientation of the toric ReSTOR IOL, defocus curve and quality of vision assessment.

The primary outcome measure will be the residual refractive cylinder.

Secondary outcome measures are as follows:

- Monocular and binocular Uncorrected and Best-corrected distance, intermediate (60cm) and near (40cm) visual acuity
- Postoperative orientation changes with the Toric ReSTOR IOL up to 3 months after surgery.
- Binocular Uncorrected and Best-corrected defocus curve (3 month visit).
- Quality of vision, measured with a subjective questionnaire.

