#### 9.3.2. Operative (Surgery)

The patient will be brought the operating room where standard phacoemulsification and IOL implantation will be performed. At the end of the procedure, a microscope photograph will be taken to document the orientation of the IOL.

Surgical findings will be recorded and any adverse events/serious adverse events (AEs/ SAEs) occurring during surgery will be noted at this visit. Any other problems during surgery and comments regarding surgery will be documented.

Any subject whose surgery is not completed successfully will be documented. These subjects will be monitored for safety but clinical performance data may be excluded from the analysis.

All study subjects will be placed on an appropriate antibiotic (Vigamox) and steroid (Durezol) drop QID for one week. A non-steroidal anti-inflammatory (Ilevro) drop will also be applied once a day for the first two weeks.

For the following three weeks, the steroid (Durezol) drop will be continued on a tapered dose.

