##### **9.4.1. Manifest Refraction**

Perform a manifest refraction with a high contrast logMAR chart under photopic lighting conditions ( $>85 \text{ cd/m}^2$ ). Document refraction results with sphere, cylinder and axis readings. If uncorrected visual acuity is not improved by manifest refraction, use zero for sphere and cylinder and draw a line through the blank for the axis.

***Note:*** Each subject should be manually refracted to his/her best correction by an ophthalmologist, optometrist, or a skilled technician using a phoropter or trial lenses.

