## **10. ANALYSIS PLAN**

### ***10.1. Analysis Data Sets***

All subjects who are enrolled in the study will be evaluated for safety. Efficacy analyses will be performed based on data from those eyes where uncomplicated Verion-LenSx guided arcuate incisions were completed.

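### Section 7.3 lets the unmasked investigator declare a patient non-evaluable on undefined medical evidence with no stated time limit, so exclusion from the primary analysis can be decided with the residual cylinder already known

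*Combined protocol and SAP*

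**What the plan says.** The last part of section 7.3 (Exclusion Criteria) reads: "The principal investigator reserves the right to declare a patient ineligible or non-evaluable based on medical evidence", where the evidence must point to the patient being unsuitable. The next paragraph adds that "subjects who become pregnant during the study will not be discontinued but their data may be excluded from analyses of effectiveness". Section 9.3.2 says that subjects whose surgery was not completed successfully will be "monitored for safety but clinical performance data may be excluded from the analysis".

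Section 3 describes a "Prospective, non-randomized, single-arm, single center, open-label study" and gives masking as none. Under section 8.1, "The primary outcome measure will be the residual refractive cylinder". Section 9.4.1 lets an ophthalmologist, optometrist or skilled technician perform the refraction and does not ask for a masked or independent assessor. Table 15.1 schedules postoperative manifest refraction at Visits 5 and 6 (1 and 3 months).

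The only definition of the efficacy set is in section 10.1: "Efficacy analyses will be performed based on data from those eyes where uncomplicated Verion-LenSx guided arcuate incisions were completed". It does not mention non-evaluable patients. Sections 9.6 and 18.2 deal with discontinuation, not with whether collected data are used.

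**The concern.** Ineligibility concerns entry to the study. Non-evaluability concerns whether the data of someone already in it will be used. Section 7.3 names both, joined by *or*, so the second word naturally reaches enrolled patients. The person holding this right works at the single site, in an open-label study, where refraction and lens orientation are recorded at 1 and 3 months. If the decision is taken after those visits, it can be influenced by the result, knowingly or not.

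The design makes this more serious. The one comparison specified in detail (section 11) sets the study mean against a literature mean and SD. There is no concurrent arm in which the same discretion would operate and partly cancel. The stated aim of a normative standard for refractive outcomes also depends on the full set of treated patients being reported. Section 8.2 expects no bias because there is a single arm, so the plan contains no safeguard against this route.

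**Working it through.** **1. Inputs.** From section 11: reference 0.40 D, SD 0.32 D, margin 0.25 D, power 0.90, alpha 0.05, 29 subjects required, 32 enrolled. From section 10.2: two-sided tests at 5%, which is one-sided 0.025 for non-inferiority.

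**2. The plan's own figure.** n per group = 2 × [SD × (z_alpha + z_power) / margin]².
- One-sided 0.05: 2 × [0.32 × (1.645 + 1.282) / 0.25]² = 28.1, so 29. This reproduces the plan.
- One-sided 0.025: 2 × [0.32 × (1.960 + 1.282) / 0.25]² = 34.4, so 35.

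The stated 29 therefore matches one-sided 0.05, not the level in section 10.2. That is a separate issue, but it is why both levels appear below.

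**3. Reading the text.**
- Deadline for a non-evaluable decision: none stated.
- List of qualifying medical evidence: none stated.
- Masked or independent review: none stated.
- Analysis of all implanted eyes, or a sensitivity analysis: none planned.
- Efficacy set in 10.1: defined by arcuate incisions, whose use at surgery is an exclusion criterion in 7.3. It cannot serve as the safeguard.

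**4. Worst-case size.** The true toric mean is put at the margin, 0.40 + 0.25 = 0.65 D, so every non-inferiority claim is false. Assumptions: 32 subjects, one gamma-distributed value each, SD 0.32 D, and the k largest values removed. The test is a pooled two-sample t, with its upper one-sided 97.5% limit compared with 0.25 D. The comparator size of 32 is assumed, because the documents do not give it.

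| Worst removed | Expected mean (D) | False claim, comparator sampled | False claim, comparator fixed at 0.40 D |
|---|---|---|---|
| 0 | 0.650 | about 2% | about 0.4% |
| 1 | 0.623 | about 5% | about 1.4% |
| 2 | 0.602 | about 9% | about 3.7% |
| 3 | 0.583 | about 14% | about 7.7% |

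The last two columns differ for a simple reason. The test uses a standard error of 0.32 × √(1/32 + 1/32) = 0.080 D. If the published mean is treated as a fixed number, only the toric mean varies, with standard error 0.32/√32 = 0.057 D, so the test starts well below its nominal level. Removing three patients shifts the mean by 0.650 − 0.583 = 0.067 D, most of one 0.080 D standard error.

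**5. Sensitivity (sampled comparator of 29).** With normal data at one-sided 0.025, the rates are 2.5%, 4.9%, 7.9% and 11.5%. With gamma data at one-sided 0.05, they are about 5%, 10%, 16% and 23%.

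**6. Effect on the normative value.** At a true mean of 0.40 D, removing the worst 1, 2 or 3 lowers the reported mean to 0.37, 0.35 and 0.33 D.

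**The case against.** The strongest reply is that the right is conditional. It requires medical evidence that the patient is unsuitable, and neither a high cylinder nor a rotated lens is listed as a ground. The sentence also closes a list of enrolment criteria, so it could be meant for screening only. A reader might infer that 7.3 states a power to exclude on outcome, at any time. The documents do not support that: the ground is medical, and the absence of a time limit is silence, not an express permission. What survives is that the evidence is undefined and is judged by someone who may know the outcome. The word *non-evaluable* also has little use if the sentence applies only at screening.

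The related clauses are weaker support than they may look. Unsuccessful surgery (9.3.2) is recorded at the operative visit, before the first postoperative refraction at 1 month, so the trigger cannot depend on the cylinder. Section 7.4 makes exclusion mandatory for aborted surgery where 9.3.2 makes it optional. That is an inconsistency to reconcile, not evidence of outcome-driven removal. Pregnancy is an objective event, and 7.3 gives a reason, its effect on refraction. Only the choice to use the exclusion is open.

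On size, the simulation removes exactly the worst patients, and the documents give no expected frequency of non-evaluable declarations. Removals unrelated to outcome would not bias the mean. Section 10.2 also allows further unspecified tests, so the comparison in section 11 is the only one specified in detail, not necessarily the only one.

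**Conclusion.** The point holds as a discretionary rule that can be used with the outcome known and that nothing else in the plan constrains. It does not show that outcome-based exclusion is intended or authorised.

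The size depends on how the literature comparator is treated. In the worst case, three removals out of 32 raise the false non-inferiority rate at one-sided 0.025 from about 2% to 14% (comparator sampled) or from about 0.4% to 7.7% (comparator fixed at 0.40 D). The higher pair should not be quoted as the error rate against a fixed published mean. Both columns rise steeply, and both are upper illustrations resting on an assumed comparator size of 32, one value per subject, equal SDs and removals that follow the outcome exactly. The direction needs less: in this design, any loss of high-cylinder patients favours the claim. A change is warranted because a clear rule costs almost nothing.

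**What to change.** - **7.3:** limit the investigator's right to declare ineligibility to the period before first-eye surgery, and delete the words *or non-evaluable*.
- **10.1:** replace the arcuate-incision wording with a primary efficacy set of all eyes implanted with a study lens that have a postoperative refraction. Editing 7.3 alone would leave the primary analysis set undefined.
- **7.4 and 9.3.2:** reconcile their data-exclusion wording with each other and with that set, including the case of a fellow eye already implanted when the other eye's surgery is aborted.
- **Pregnancy:** keep these subjects in the primary analysis, with one sensitivity analysis omitting refractions taken during pregnancy.
- **Later-discovered ineligibility:** report it as a protocol deviation, with results shown with and without that patient.

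The cost is a wording amendment to four sections, one sensitivity analysis and, where needed, a with-and-without comparison. The small downside is that an occasional truly ineligible eye stays in and adds a little noise.

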## 8. STUDY DESIGN

### 8.1. Study Design

This study is a prospective, single center, open clinical trial to evaluate visual acuity at distance, intermediate and near as well as rotational stability of the Toric-ReSTOR IOL for 3 months after cataract surgery. Patients will be bilaterally implanted, with the Toric ReSTOR +2.5D model implanted in the dominant eye and the Toric ReSTOR +3.0D model implanted in the non-dominant eye. Patients will self-select for multifocal implantation. Toric IOL calculations will be completed with the Alcon Toric calculator, including the Barrett adjustment for posterior corneal astigmatism. The default surgically-induced astigmatism (0.1D) will be used for all calculations. Results from this study will be compared to outcomes data in the literature for the non-toric ReSTOR IOLs. Quality of vision will be measured using a validated, Rasch-scored questionnaire and compared to data available in the literature for non-toric ReSTOR lenses.

Subjects will be assessed pre-operatively and at 1 day, 1 week, 1 month and 3 months post-operatively.

Clinical evaluations will include measurement of visual acuity, manifest refraction, orientation of the toric ReSTOR IOL, defocus curve and quality of vision assessment.

The primary outcome measure will be the residual refractive cylinder.

Secondary outcome measures are as follows:

- Monocular and binocular Uncorrected and Best-corrected distance, intermediate (60cm) and near (40cm) visual acuity
- Postoperative orientation changes with the Toric ReSTOR IOL up to 3 months after surgery.
- Binocular Uncorrected and Best-corrected defocus curve (3 month visit).
- Quality of vision, measured with a subjective questionnaire.

### 8.2. Methods Used to Minimize Bias

As a single-arm study there is no expected bias. Patient selection will be based on the patient's interest and the surgeon's opinion as to whether they are a suitable candidate for multifocal toric lens implantation.

The measurement of visual acuity will be conducted in a systematic fashion to minimize bias. Individuals conducting visual acuity measures will be instructed to perform the

same testing in the same fashion for all subjects, with the same level of encouragement to subjects. Questions regarding quality of vision will be asked in a similar manner to all patients.

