## **11. SAMPLE SIZE JUSTIFICATION**

Data in the literature suggests that the ReSTOR non-toric IOLs (+3.0D and +2.5D) implanted in a group of eligible eyes showed a residual refractive cylinder of  $0.40D \pm 0.32D$ . (Gundersen KG, Potvin R. Comparison of visual outcomes and subjective visual quality after bilateral implantation of a diffractive trifocal intraocular lens and blended implantation of apodized diffractive bifocal intraocular lenses. Clin Ophthalmol. 2016 May 10;10:805-11). We are looking for the toric IOLs to be non-inferior. We powered the study using that mean and SD, a power of 0.9, an alpha of 0.05, and a 0.25D non-inferiority margin. The mean residual refractive cylinders will be compared using a t-test between the two groups, with the mean and SD from the literature (blended bifocal group) and the mean and SD from the current study. The required sample size is 29 subjects. Allowing for 10% dropout we will plan to enroll 32 subjects.

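### The plan says a single-arm study has no expected bias; this is false for an unmasked, self-selected cohort tested against a published mean, and neither the primary refraction nor exclusion decisions are protected

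*Combined protocol and SAP*

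**What the plan says.** Section 8.2 (Methods Used to Minimize Bias) opens with "As a single-arm study there is no expected bias". It goes on: "Patient selection will be based on the patient's interest and the surgeon's opinion as to whether they are a suitable candidate" for the lens. It then standardises two things: acuity testing, with the same method and encouragement for every subject, and the way quality-of-vision questions are asked.

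Other sections describe the design and the test:

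- Section 3 (General Information): "Prospective, non-randomized, single-arm, single center, open-label study". Masking and control article are both given as none.
- Section 8.1: "Patients will self-select for multifocal implantation", "Results from this study will be compared to outcomes data in the literature for the non-toric ReSTOR IOLs", and "The primary outcome measure will be the residual refractive cylinder".
- Section 11: "The mean residual refractive cylinders will be compared using a t-test between the two groups, with the mean and SD from the literature" on one side and those of the current study on the other, with a 0.25 D non-inferiority margin.
- Section 9.4.1: the refraction is done manually by an ophthalmologist, optometrist or skilled technician, under a stated chart type and lighting level. Zero is entered for sphere and cylinder when refraction does not improve uncorrected acuity.
- Sections 9.2, 9.3.5 and 9.3.6: lens orientation is documented by a microscope photograph at the end of surgery and by dilated Verion photographs at 1 and 3 months. No reader or reading conditions are named.
- Section 7.3: "The principal investigator reserves the right to declare a patient ineligible or non-evaluable based on medical evidence" of unsuitability for the trial. No time limit is set on that decision. Sections 7.3 (pregnancy) and 9.3.2 (surgery not completed successfully) also say that data may be excluded.

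**The concern.** Having one arm removes one kind of bias only: differential handling of concurrent arms. Three other kinds remain. Selection bias can arise because the patient's interest and the surgeon's opinion decide who enters. Assessment bias can arise because the examiner is not masked. External-comparison bias can arise because the other group was recruited, operated on and refracted elsewhere. The third matters most here, because the Section 11 test is a between-group comparison that attributes the whole difference in means to the lens.

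The sentence also bears on what the plan protects. The measures in Section 8.2 concern acuity and the questionnaire, both secondary. The primary endpoint comes from an examiner's judgement. The documents do not say whether that examiner may be the surgeon, or may see the toric plan or earlier refractions. A decision that a patient is non-evaluable could be taken after the cylinder is known. With a margin of 0.25 D, a modest systematic shift could decide the result in either direction. Because the stated objective is a normative standard, readers will also rely on the estimate itself.

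**Working it through.** **Inputs.** From Section 11: published cylinder 0.40 D with SD 0.32 D, margin 0.25 D, power 0.90, alpha 0.05, 29 subjects required. From Section 10.2: all tests two-sided at 5%. Assumed, because the documents do not give them: the bias sizes, the size of the published group (taken as 29), the same SD in both groups, and one value per subject.

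**Step 1: the plan's own figure.** The two-sample non-inferiority formula with a true difference of zero and one-sided alpha 0.05 is

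n per group = 2 × [0.32 × (1.645 + 1.282) / 0.25]² = 28.1, rounded up to 29.

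This matches Section 11; the exact t version also gives 29. Testing against a fixed value instead would need only 15 or 16. The sample size therefore treats the published group like a second arm of 29. At one-sided 0.025, the non-inferiority counterpart of a two-sided 5% test, the formula gives 34.4, rounded up to 35 (36 by the t version). Both alphas are carried below.

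**Step 2: standard error.** SE = 0.32 × √(2/29) = 0.084 D.

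**Step 3: favourable bias, true difference at the margin.** The false non-inferiority rate is 1 − Φ(z − bias/SE).

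| Bias (D) | bias/SE | One-sided 5% | One-sided 2.5% |
|---|---|---|---|
| 0 | 0 | 5% | 2.5% |
| 0.05 | 0.595 | 1 − Φ(1.050) = 14.7% | 1 − Φ(1.365) = 8.6% |
| 0.10 | 1.190 | 1 − Φ(0.455) = 32.5% | 1 − Φ(0.770) = 22.1% |
| 0.125 | 1.487 | 1 − Φ(0.157) = 43.7% | 1 − Φ(0.473) = 31.8% |

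The noncentral t with 56 degrees of freedom gives 14.5%, 31.9% and 43.0% at one-sided 5%, and 8.5%, 21.5% and 30.9% at one-sided 2.5%. The choice of approximation does not matter.

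**Step 4: unfavourable bias, no true difference.** By the noncentral t at one-sided 5%, power is 90.2% without bias, 76.0% with 0.05 D and 54.7% with 0.10 D. The normal formula, Φ((0.25 − bias)/SE − 1.645), gives 90.8%, 76.9% and 55.6%.

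**Step 5: range for the unknown size of the published group.** At the other extreme, the published mean is treated as known exactly. Then SE = 0.32/√29 = 0.059 D, and the Step 3 rates at one-sided 5% become 21%, 52% and 68%. A published group larger than 29 therefore makes the test more sensitive to a fixed bias.

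**Step 6: what a tipping-point line would show.** Non-inferiority holds while (observed mean − published mean) + z × SE is below 0.25 D. If the observed mean equalled 0.40 D with the SE of Step 2, the published mean would have to fall by 0.25 − 1.645 × 0.084 = 0.11 D to overturn the conclusion at one-sided 5%, or by 0.25 − 1.960 × 0.084 = 0.085 D at one-sided 2.5%.

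**The case against.** A reader might infer that the plan uses no safeguard at all. The documents do not support that. Section 8.2 standardises acuity testing and questioning, and Section 9.4.4 tells staff not to rephrase questionnaire items. Section 9.4.1 fixes the chart, lighting, recording rule and examiner types for refraction, and Section 9.3 says site personnel will be trained. Stored photographs give orientation a lasting record. What is missing is narrower: masking of the refraction and of the photograph reading, and a time limit on exclusion decisions.

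A reader might also infer that the trial is biased in favour of the toric lens. Nothing in the documents fixes the direction or size of any bias, and no mechanism is given by which choosing a multifocal lens would change residual cylinder. Step 3 is a worst case, with the true difference exactly at the margin, whereas the sample size reproduces with a true difference of zero. The figures are illustrations, not predictions.

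The investigator's discretion should not be read as arbitrary either: Section 7.3 ties it to medical evidence of unsuitability. Only its timing is open.

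Finally, masking is a partial remedy. Every eye receives a toric lens, so a masked refractionist still knows the lens type, and masking cannot make this cohort comparable with the published one. The end-of-surgery microscope image may be recognisable beside the Verion photographs. The plan is also open about being single-arm, open-label and compared with literature. All of this stands and limits the claim, but none of it makes the opening sentence of Section 8.2 true.

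**Conclusion.** The concern holds in limited form. The statement of no expected bias claims a property that the design in Sections 3, 8.1 and 11 does not have. Standardised procedures exist, including for refraction, but the primary refraction and the orientation reading are unmasked, and non-evaluable decisions need not precede sight of outcomes.

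The size can only be illustrated. Under the assumptions in the working, a favourable bias of 0.05 to 0.125 D takes the false non-inferiority rate to about 15–44% against a nominal 5%, or about 9–32% against a nominal 2.5%. An unfavourable bias of 0.05 to 0.10 D takes power from 90% to about 76–55% at one-sided 5%. The exact values depend on the size of the published group, which the plan does not state. It is a point that should be corrected; it does not show that the study's result will be wrong.

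**What to change.** 1. Replace the opening sentence of Section 8.2 with the actual bias sources: self-selection and surgeon selection, unmasked assessment, discretionary exclusion, and comparison with a published group.
2. Require any non-evaluable or exclusion decision to be recorded, with its reason, before that patient's postoperative refraction is seen, and list all such exclusions in the report.
3. Measure the orientation photographs in random order with visit labels hidden, noting that the end-of-surgery microscope image may remain recognisable.
4. Report the shift in the published mean that would overturn non-inferiority, as in Step 6, and describe the result as a comparison with a published value.
5. Where existing staffing allows, withhold the toric plan and earlier refractions from the refractionist at Visits 5 and 6. The documents do not say who refracts, so this is conditional.

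The cost is revised wording, small workflow changes and one extra analysis line. Items 1 to 4 need no extra patients, visits or staff. Items 2, 3 and 5 reduce bias within the study; items 1 and 4 disclose the limits of the external comparison, which no masking can remove.
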